4.5.4. Cohort A and Cohort A1 Exploratory Efficacy Variables

The following exploratory variables are for both Cohort A and Cohort A1. Some of the endpoints will mature and be assessed after all subjects complete the study. For continuous variables the analysis only applies to subjects who have a positive central lab SARS-CoV-2 RT-qPCR test (based on observed data) during the EAP.

Exploratory Variables	Type
Proportion of baseline-seronegative subjects who have a first RT-qPCR confirmed SARS-CoV-2 infection in the follow-up period (i.e. after Day 29 visit)	B
Proportion of baseline-seronegative subjects who become seropositive (based on central lab test) up to day 57 (Note: For post-treatment serology, only antibody assay(s) that do not bind to REGN10933 or REGN10987 will be used to define the endpoint)	B
Proportion of baseline-seropositive subjects (based on central lab test) who subsequently have a positive SARS-CoV-2 RT-qPCR and symptomatic (strict-term) SARS-CoV-2 infection during the EAP	B
Proportion of subjects with negative RT-qPCR (based on central lab test) regardless of the serology status at baseline who subsequently have a positive SARS-CoV-2 RT-qPCR and symptomatic (strict-term) SARS-CoV-2 infection during the EAP	B

Proportion of baseline-seronegative or baseline-seropositive subjects with negative RT-qPCR (based on central lab test) who subsequently have a positive SARS-CoV-2 RT-qPCR and symptomatic (strict-term) SARS-CoV-2 infection during the EAP	B
Proportion of baseline-seropositive subjects (based on central lab test) who subsequently have a positive SARS-CoV-2 RT-qPCR and symptomatic (broad-term) SARS-CoV-2 infection during the EAP	B
Proportion of subjects with negative RT-qPCR (based on central lab test) regardless of serology status at baseline who subsequently have a positive SARS-CoV-2 RT-qPCR and symptomatic (broad-term) SARS-CoV-2 infection during the EAP	B
Proportion of baseline-seronegative or baseline-seropositive subjects with negative RT-qPCR (based on central lab test) who subsequently have a positive SARS-CoV-2 RT-qPCR and symptomatic (broad-term) SARS-CoV-2 infection during the EAP	B
Proportion of baseline-seropositive subjects (based on central lab test) who subsequently have a positive SARS-CoV-2 RT-qPCR and symptomatic (CDC definition) SARS-CoV-2 infection during the EAP	B
Proportion of subjects with negative RT-qPCR (based on central lab test) regardless of serology status at baseline who subsequently have a positive SARS-CoV-2 RT-qPCR and symptomatic (CDC definition) SARS-CoV-2 infection during the EAP	B
Proportion of baseline-seronegative or baseline-seropositive subjects with negative RT-qPCR (based on central lab test) who subsequently have a positive SARS-CoV-2 RT-qPCR and symptomatic (CDC definition) SARS-CoV-2 infection during the EAP	B
Proportion of baseline-seropositive subjects (based on central lab test) who subsequently have a positive SARS-CoV-2 RT-qPCR during the EAP	B
Time-weighted average of viral load (log10 copies/mL) from the first positive SARS-CoV-2 RT-qPCR in NP swab sample (that has an onset during the EAP) until third weekly visit after the first positive test in seropositive subjects (based on central lab test) during the EAP	C
Time-weighted average of viral load (log10 copies/mL) from the first positive SARS-CoV-2 RT-qPCR in NP swab sample (that has an onset during the EAP) until the second weekly visit after the first positive test in seropositive subjects (based on central lab test) during the EAP	C
Area under the curve (AUC) in viral load (log10 copies/mL) in NP swab samples from the first positive SARS-CoV-2 RT-qPCR NP swab sample until the first confirmed negative test, in seropositive subjects (based on central lab test) that has an onset during the EAP	C
Note: Only for RT-qPCR positive subjects during the EAP with confirmed negative tests in the seronegative mFAS	
Proportion of subjects in placebo group who have a RT-qPCR confirmed SARS-CoV-2 infection (regardless of symptoms) during the EAP by the status of household members participating in study R10933-10987-COV-2067 and receiving REGN10933+REGN10987 or whose household member did not receive treatment with REGN10933+REGN10987	B
Proportion of subjects who have a RT-qPCR confirmed SARS-CoV-2 infection (regardless of symptoms) during the EAP by the status of household members participating in study R10933-10987-COV-2067 and receiving REGN10933+REGN10987	B
Proportion of subjects who have a RT-qPCR confirmed SARS-CoV-2 infection (regardless of symptoms) during the EAP by the status of household members receiving an approved monoclonal antibody treatment for COVID-19	B

Proportion of subjects who have a RT-qPCR confirmed SARS-CoV-2 infection (regardless of symptoms) during the EAP by the status of household members receiving an approved monoclonal antibody treatment for COVID-19 or REGN10933+REGN10987 in study R10933-R10987-COV-2067	B
Maximum RT-qPCR viral load (log10 copies/mL) in NP swab samples during the EAP in subjects who have asymptomatic infection during the EAP	C
Maximum RT-qPCR viral load (log10 copies/mL) in NP swab samples during the EAP in subjects who have symptomatic infection during the EAP	C
Maximum RT-qPCR viral load (log10 copies/mL) in NP swab samples during the EAP in subjects who have a medically attended visit	C

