### 5.2. Efficacy Variables

The efficacy variables include measurements or test results for individual subjects of the following:

- A positive SARS-CoV-2 infection (ie, a positive RT-qPCR) will be defined based on any available RT-qPCR result (either NP, nasal or saliva) which is reported as “detected”. A negative infection (ie, a negative RT-qPCR) will be defined based on all available RT-qPCR results (either NP, nasal or saliva) which are reported as “not detected”
- Viral load ( $\log_{10}$  copies/mL) from RT-qPCR test
- Asymptomatic SARS-CoV-2 infection: positive RT-qPCR result of NP swab sample without any of the strict-term or broad-term SARS-CoV-2 infection signs and symptoms (specified in Section [9.2.2.2](#)) within the EAP
- Symptomatic infection based on strict-term SARS-CoV-2 infection signs and symptoms (for secondary endpoint): Positive strict-term symptomatic infection defined as SARS-CoV-2 infection signs and symptoms (specified in Section [9.2.2.2](#)) and a positive RT-qPCR that occurs within the EAP
- Symptomatic infection based on broad-term SARS-CoV-2 infection signs and symptoms (for secondary endpoints): Positive broad-term symptomatic infection defined as SARS-CoV-2 infection signs and symptoms (specified in Section [9.2.2.2](#)) and a positive RT-qPCR that occurs within the EAP
- Symptomatic infection based on CDC definition SARS-CoV-2 infection signs and symptoms (for secondary endpoints): Positive broad-term symptomatic infection defined as SARS-CoV-2 infection signs and symptoms (specified in Section [9.2.2.2](#)) and a positive RT-qPCR that occurs within the EAP
- Medically attended visits to ED or UCC due to SARS-CoV-2 infection: number of visits that occur after a positive RT-PCR result within the EAP
- Hospitalization due to SARS-CoV-2 infection (hospitalization status and days in hospital) within the EAP

- Days absent from daily responsibilities (eg, days missed from work, school, childcare, or eldercare) due to SARS-CoV-2 infection within the EAP
- Occurrence of laboratory-confirmed SARS-CoV-2 infection during follow-up period collected from spontaneously reported AEs

Detailed descriptions for assessing COVID-19 signs and symptoms and their temporal relationship with lab confirmed SARS-CoV-2 infection is provided in Section [9.2.2.2](#).

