9. Subjects who are RT-qPCR positive at the end of the EAP will continue to have samples collected weekly (NP swab; central lab) for RT-qPCR. Subjects will continue assessments/sample collections until 2 negative RT-qPCR test results have been obtained  $\geq 24$  hours apart (all samples must be negative). Subjects who are RT-qPCR negative at the end of the EAP will have samples collected only if they become symptomatic with COVID-19 in the follow-up period. If a subject is hospitalized for suspected COVID-19, every effort should be made by the site personnel to collect, as soon as possible, a NP swab sample for central lab SARS-CoV-2 RT-qPCR testing. In subjects where it is not possible to have samples collected for assessment in the central laboratory, study site personnel will attempt to obtain and record information about all SARS-CoV-2 tests conducted in local laboratories associated with other medical facilities, including result(s), name of the assay(s) and whether the laboratory(ies) conducting the assays is a CLIA certified (or equivalent) laboratory. The positive test result should be recorded as concomitant procedures.

10. For subjects who are not in the sentinel group (subset 1; completed), vital signs will be monitored on site as follows: Safety group (subset 2; completed): at baseline predose and then every hour for 2 hours after study drug administration and a phone call on day 4 to assess AEs, specifically injection site reactions and hypersensitivity; all other subjects (subset 3): at baseline and 1 hour after study drug administration. All subjects will be advised to call the site if signs/symptoms of injection site or hypersensitivity reactions occur. If the subject experiences a true medical emergency, they should visit their local hospital ED and contact the site personnel later.
11. The investigator may perform a targeted physical exam, request an exam and/or vital signs at any time. These assessments can be performed using a clinic visit or a remote visit with the investigator or sub-investigator, or designee (ie, nurse practitioner in countries where allowed by local law).
12. For all women of childbearing potential (WOCBP) and girls at or beyond menarche, except subjects with a confirmed pregnancy. If the local urine pregnancy test is positive, the site must perform a serum pregnancy test for confirmation.

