13. Samples for drug concentration and, immunogenicity, and laboratory testing will be collected based on the subject subset designation as indicated in [Table 4](#)
14. The serology test results will not be communicated to the sites. The sponsor's blinded study team will not have access to post-baseline results associated with subject identification until after the database is locked.
15. During each scheduled or unscheduled visit/contact, the investigator or designee will query subject about AEs in general (see Section [10.1.1](#)) and evaluate if the AEs are associated with SARS-CoV-2 infection, including fever (see Section [9.2.2.2](#)). The investigator should recommend that subjects (themselves or by their parent/guardian) measure their temperature daily during EAP, approximately at the same time, and also every time when the subject feels feverish, chills, or sick. Subjects with symptomatic SARS-CoV-2 infection should be queried on their symptoms weekly until symptoms resolve, even during follow-up period, then follow the regular schedule.
16. The information for the household assessment, including household members who receive an EUA approved monoclonal antibody treatment for COVID-19 or household members participating in the R10933-10987-COV-2067 study, should preferably be collected at the baseline visit. There will be a follow-up assessment at day 29.
17. All subjects will have a weekly NP swab sample collected during the EAP. Only subjects who are RT-qPCR positive will continue to have weekly NP swab samples collected during the follow-up period until 2 consecutive negative ( $\geq 24$  hr) RT-qPCR results or the end of study visit.
18. Only for RT-qPCR positive subjects (cohort A and cohort B): Complete assessments from the time the subject first becomes RT-qPCR positive or from the time they develop symptoms suspected to be COVID-19 (later confirmed by RT-qPCR positive results) until the subject has had 2 negative tests or COVID-19 related symptoms have resolved (whichever lasts longer), or until the end of study visit.

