**9.1.6. Unscheduled Visits**

All attempts should be made to keep subjects on the study schedule. Unscheduled visits may be necessary to repeat testing following abnormal laboratory results, for follow-up of AEs, for SARS-CoV-2 RT-qPCR and serology testing when subjects experience symptoms consistent with SARS-CoV-2 infection (per the broad-term list specified in Section 9.2.2.2), or for any other reason, as warranted.

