5.7.4. Analyses of Other Secondary and Exploratory Efficacy Variables

Other secondary efficacy endpoints will be analyzed by type of endpoint defined in Sections 4.5.2 to 4.5.8 for all cohorts. The analysis methods for key secondary efficacy endpoints in both cohort A and cohort B will also be applied to exploratory endpoints in both cohort A and cohort B if appropriate. Otherwise, the primary approach to the data will be descriptive statistics. For the comprehensive evaluation of efficacy, nominal p-values may be reported. Raw data descriptive statistics will also be presented.

Other secondary efficacy and exploratory endpoints for cohort A1 and cohort B1 may also be analyzed by type of endpoint. If the sample size is sufficient, continuous variables will be summarized by the descriptive statistics (e.g., n, mean, SD, Q1, median, Q3, minimum and maximum, etc.). Binary variables will be summarized using the number and percentage of subjects in each treatment group. No statistical hypothesis testing will be performed for cohort A1 and cohort B1. This approach may also be applied to adolescent subjects.

Binary Endpoints

Binary endpoints in cohort A and cohort B will be analyzed by applying the same approach used for the primary efficacy endpoints.

For endpoints regarding viral loads, visits with missing viral load (\log_{10} copies/mL) in NP swab samples will not be included in the analyses. For binary endpoints regarding the index case or household members linkage to R10933-10987-COV-2067 or subjects in cohort B, and endpoints regarding the medically attended visits, Fisher's exact test will be used. KM curves will be used to assess the exploratory endpoint of proportion of baseline-seronegative subjects who have a first RT-qPCR confirmed SARS-CoV-2 infection in the follow-up period.

Continuous Endpoints

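### The follow-up endpoint named first RT-qPCR confirmed infection rests almost entirely on symptom-triggered swabs, so its curve can overstate protection against infection after day 29

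*SAP*

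**What the plan says.** The endpoint appears in Protocol 4.1.4 and in SAP 4.5.4, where it reads "Proportion of baseline-seronegative subjects who have a first RT-qPCR confirmed SARS-CoV-2 infection in the follow-up period", counted after the day 29 visit. SAP 5.7.4 adds that "KM curves will be used to assess the exploratory endpoint of proportion of baseline-seronegative subjects who have a first" confirmed infection in follow-up.

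The swab rules are in the schedule-of-events footnotes (Protocol 9.1.1):

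- EAP: "All subjects will have a weekly NP swab sample collected during the EAP" (footnote 17).
- Follow-up, subjects already positive: "Only subjects who are RT-qPCR positive will continue to have weekly NP swab samples collected during the follow-up period" (footnote 17).
- Follow-up, subjects negative at day 29: "Subjects who are RT-qPCR negative at the end of the EAP will have samples collected only if they become symptomatic with COVID-19" in that period (footnote 9). SAP 10.2.1 repeats this. The pediatric footnotes (Protocol 9.1.3, SAP 10.2.3) give the same rule.

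Protocol 5.2 names the source of the follow-up variable: "Occurrence of laboratory-confirmed SARS-CoV-2 infection during follow-up period collected from spontaneously reported AEs". Protocol 9.1.6 allows unscheduled RT-qPCR and serology testing "when subjects experience symptoms consistent with SARS-CoV-2 infection", and leaves room for unscheduled visits for other reasons. RT-qPCR negative subjects have a monthly adverse event assessment in follow-up (footnote 19), with general questioning and no symptom prompts (Protocol 10.1.1).

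I found no statement in either document that asymptomatic infections go largely undetected after day 29, or how untested subjects are counted in the curve.

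**The concern.** The same phrase means two things. In the EAP an RT-qPCR confirmed infection is any infection that a weekly swab can find. In follow-up, the subjects who keep weekly swabs are already positive and cannot have a first infection. Those who can have one are swabbed when symptoms bring them forward. Elsewhere the plan separates symptomatic infection from infection regardless of symptoms (SAP 4.5.2), so a reader would take the unqualified name to mean any infection.

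This matters because detection depends on something the drug may change. That the drug prevents symptoms in infected people is the cohort B hypothesis (Protocol 3.1), and Protocol 11.2.2 plans for a relative risk of 0.5. If that ratio held for infections in follow-up (an assumption, since cohort B is infected when dosed), a drug with no effect on infection would show an apparent ratio of 0.5. A Kaplan-Meier curve over follow-up invites a reading as duration of protection against infection.

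**Working it through.** **No planned figure.** The documents give no rate, power or sample size for this endpoint, so there is nothing to reproduce for it. I checked the administrative inputs instead.

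**1. Input check.** Protocol 3.2.5 gives 8/223 symptomatic on placebo and 0/186 on active. 8/223 = 3.6%. Fisher's exact test gives p = 0.0091 and the exact upper limit of the odds ratio is 0.689. These match the stated 3.6%, p<0.01 and 0.69.

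**2. Infected subjects.** Protocol 3.2.6 prints 21 and 9 as viral-load denominators among the infected. I assume that these are all the infections.

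- In favour: 21 + 9 = 30, as in the roughly 30 events of Protocol 11.2. Also (9/186)/(21/223) = 0.514, close to the 50% reduction in 11.2.1.
- Against: the same section reports 10.3% and 5.4% infected by day 8. On full denominators that is 0.103 × 223 = 23 and 0.054 × 186 = 10, slightly more than 21 and 9.

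**3. Symptomatic share of infections, s.**

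- Placebo: 8/21 = 0.381 (exact 95% CI 0.18 to 0.62), or 8/23 = 0.348 on the day 8 reading.
- Active: 0/9 = 0 (exact 95% CI 0 to 0.336).
- Fisher's test of 8/21 against 0/9: p = 0.067.

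**4. Bias.** If only symptomatic infections are detected, detected risk = P(infection) × s, so

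apparent ratio = true ratio × s_active / s_placebo.

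With s_placebo held at 0.381:

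| s_active | apparent ratio, true ratio 1 | apparent ratio, true ratio 0.514 |
|---|---|---|
| 0 | 0 | 0 |
| 0.10 | 0.26 | 0.13 |
| 0.20 | 0.53 | 0.27 |
| 0.30 | 0.79 | 0.40 |
| 0.336 | 0.88 | 0.45 |
| 0.381 | 1.00 | 0.51 |

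Letting the placebo share move to its own lower limit as well, 0.336/0.181 = 1.86, so the data do not exclude a bias in the other direction.

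**5. How often it would mislead.** Simulation with no true effect on infection, 1248/2 = 624 independent subjects per arm, s_placebo = 0.381, two-sided Fisher test at 0.05, 4000 runs. The follow-up infection risk is an assumption.

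| true risk, both arms | s_active 0 | 0.10 | 0.20 | 0.381 |
|---|---|---|---|---|
| 2% | 33% | 13% | 5% | 2% |
| 5% | 98% | 53% | 19% | 3% |
| 10% | 100% | 90% | 41% | 3% |

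Entries are the share of trials with a nominally significant difference in detected infections. At 5% risk each arm has 624 × 0.05 = 31 infections. About 12 are detected on placebo, and 0, 3 or 6 on active at shares of 0, 0.10 or 0.20.

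**6. Waning.** Protocol 3.2.1 assumes a 21-day half-life. From day 29 to day 57 is 28/21 = 1.33 half-lives, leaving about 40% of the day 29 concentration. To day 225 it is 196/21 = 9.33 half-lives, leaving about 0.2%. Shares from the 28 days after dosing should not be carried unchanged through follow-up.

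**The case against.** The strongest reply is that the plan already covers most of this.

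- **Symptomatic infection in follow-up is already an endpoint** (Protocol 4.1.3, safety endpoints) and is summarized by arm and period (Protocol 11.4.5.1). No objective claims duration of PCR-defined protection. This stands and lowers the stakes. It also makes the unqualified name harder to defend, since one endpoint says symptomatic and this one does not.
- **A symptom-independent measure exists.** SAP 4.5.4 has seroconversion up to day 57, restricted to assays that do not bind the study antibodies. That covers the weeks when symptom suppression should be strongest. This stands in part: it counts EAP infections too, and stops at day 57 of a follow-up running to day 225.
- **Ascertainment is not purely symptomatic.** A reader might infer from footnote 9 that the curve can contain nothing but symptomatic cases. The documents do not go that far. Protocol 5.2 draws on reported adverse events, SAP 5.8.1 has a category for asymptomatic COVID-19 events, and unscheduled visits have a catch-all reason. Detection is mostly, not exclusively, symptom-driven.
- **The numbers are thin.** They come from 30 infections in the EAP, with the caveat on 21 and 9 above. This stands.
- **The endpoint is exploratory**, outside both testing hierarchies, with at most nominal p-values. This stands.

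**Conclusion.** The point holds as one of labelling and interpretation. Under the planned swab rules the endpoint cannot support a conclusion about infection regardless of symptoms after day 29, and if the drug suppresses symptoms the curve can overstate protection.

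A reader might infer that the drug will falsely appear to prevent infection, or that 0 to 0.88 bounds the apparent ratio when the true ratio is 1. Neither is supported. The difference in symptomatic share is not established (p = 0.067), that range fixes the placebo share at 0.381, and the shares come from the EAP. The direction shown is the expected one, its size is unknown, and it should shrink as concentrations fall. A bias that changes over time can also distort the shape of the curve.

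The primary and key secondary results concern the EAP, with weekly swabs for all, and are not affected. The case for relabelling does not depend on the size of the bias.

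**What to change.** **Cohorts A and A1.** In SAP 4.5.4 and 5.7.4, and Protocol 4.1.4 to match:

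- rename the endpoint and its curve *first symptomatic (symptom-triggered) RT-qPCR confirmed infection in follow-up*;
- state that asymptomatic infections are not systematically ascertained after day 29, and limit the conclusion accordingly;
- align it with the existing symptomatic-infection endpoint (Protocol 4.1.3 and 11.4.5.1), so that the two counts agree or any difference is explained.

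This costs text only.

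**Cohort A only.** Add a supportive analysis of post-EAP anti-N seroconversion in subjects who were RT-qPCR negative through day 29 and anti-N negative at day 29. Use the day 57 sample and the later scheduled one (end of study, as the extracted table reads; its column alignment is lost). Apply the SAP 4.5.4 rule on assays that do not bind the drug; SAP 3.1 already names an anti-N assay. The cost is SAP text and analysis of samples already in the schedule. Anti-N may wane or be blunted by treatment, which would bring back arm-dependent detection, so the result is supportive only.

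Cohort A1 cannot have this analysis: Protocol 9.1.4 limits pediatric serology to baseline and day 29, with less in the smallest children.

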- Proportion of baseline-seropositive subjects (based on central lab test) who subsequently have a positive SARS-CoV-2 RT-qPCR during the EAP
- Time-weighted average of viral load ( $\log_{10}$  copies/mL) from the first positive SARS-CoV-2 RT-qPCR in NP swab samples (that has an onset during the EAP) until third weekly visit after the first positive test in seropositive subjects (based on central lab test) during the EAP
- Time-weighted average of viral load ( $\log_{10}$  copies/mL) from the first positive SARS-CoV-2 RT-qPCR in NP swab samples (that has an onset during the EAP) until the second weekly visit after the first positive test in seropositive subjects (based on central lab test) during the EAP
- Area under the curve (AUC) in viral load ( $\log_{10}$  copies/mL) in NP swab samples from the first positive SARS-CoV-2 RT-qPCR NP swab sample until the first confirmed

negative test, in seropositive subjects (based on central lab test) that has an onset during the EAP

- Proportion of subjects in the placebo group who have a RT-qPCR confirmed SARS-CoV-2 infection (regardless of symptoms) during the EAP by the status of household members participating in study R10933-10987-CoV-2067 and receiving REGN10933+REGN10987 or whose household member did not receive treatment with REGN10933+REGN10987
- Proportion of subjects who have a RT-qPCR confirmed SARS-CoV-2 infection (regardless of symptoms) during the EAP by the status of household members participating in study R10933-10987-CoV-2067 and receiving REGN10933+REGN10987
- Proportion of subjects who have a RT-qPCR confirmed SARS-CoV-2 infection (regardless of symptoms) during the EAP by the status of household members receiving an approved monoclonal antibody treatment for COVID-19
- Proportion of subjects who have a RT-qPCR confirmed SARS-CoV-2 infection (regardless of symptoms) during the EAP by the status of household members receiving an approved monoclonal antibody treatment for COVID-19 or REGN10933+REGN10987 in study R10933-10987-CoV-2067
- Maximum RT-qPCR viral load ( $\log_{10}$  copies/mL) in NP swab samples during the EAP in subjects who have asymptomatic infection during the EAP
- Maximum RT-qPCR viral load ( $\log_{10}$  copies/mL) in NP swab samples during the EAP in subjects who have symptomatic infection during the EAP
- Maximum RT-qPCR viral load ( $\log_{10}$  copies/mL) in NP swab samples during the EAP in subjects who have a medically attended visit

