3.1. The Efficacy Analysis Sets

Seronegative Modified Full Analysis Set (Seronegative mFAS-A) – Cohort A

The seronegative modified full analysis set for Cohort A (Seronegative mFAS-A) includes all randomized subjects aged 12 years and older who are laboratory confirmed negative for SARS-CoV-2 (per central lab PCR test) and who test negative for antibodies for SARS-CoV-2 (per central lab serology testing) at baseline.

Subjects included in the administrative assessment analysis are excluded from the Seronegative mFAS-A population.

Subjects will be analyzed based on the randomized treatment assignment. The seronegative mFAS-A population is the primary analysis population for the primary and secondary endpoints for Cohort A of this study unless specified otherwise.

Note: There are three antibody assays used for serology test: EuroImmun anti-S IgA, EuroImmun anti-S IgG, and Abbott anti-N IgG (Architect). Seronegative is defined as all available test results are negative. Seropositive is defined as 1 or more available test results are positive.

Seronegative Modified Full Analysis Set (Seronegative mFAS-A1) – Cohort A1

The seronegative modified full analysis set for Cohort A1 (seronegative mFAS-A1) includes all randomized subjects aged less than 12 years who are laboratory confirmed negative for SARS-CoV-2 (per central lab PCR test) and who test negative for antibodies for SARS-CoV-2 (per central lab serology testing) at baseline.

Subjects will be analyzed based on the randomized treatment assignment. The efficacy endpoints for Cohort A1 will be analyzed using the seronegative mFAS-A1 unless specified otherwise.

Seronegative Modified Full Analysis Set (Seronegative mFAS-B) – Cohort B

The seronegative modified full analysis set for Cohort B (seronegative mFAS-B) includes all randomized subjects aged 12 years and older who have laboratory confirmed positive tests at baseline for SARS-CoV-2 RT-qPCR and negative SARS-CoV-2 serology (both based on central lab testing) at baseline and are asymptomatic. Subjects will be analyzed based on the randomized treatment assignment. The primary and secondary efficacy endpoints for cohort B will be analyzed using the seronegative mFAS-B unless specified otherwise.

Seronegative Modified Full Analysis Set (Seronegative mFAS-B1) – Cohort B1

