3. At the screening/baseline visit, the window for baseline pre-dose PK-ADA sample collection is as close to administration of study drug as is reasonable.
4. Whole blood samples for hematology and blood chemistry will be analyzed at central lab.
5. Pediatric subjects who prematurely discontinue the study should have sample collection listed in the ET visit before exiting the study.
6. A PK-ADA serum sample will be collected as soon as possible or within 7 days of receiving the first positive SARS-CoV-2 RT-qPCR result for cohort A pediatric subjects.
7. A PK-ADA serum sample will be collected as soon as possible or within 7 days of first new positive SARS-CoV-2 RT-qPCR result after achieving 2 consecutive negative results for all pediatric subjects.
8. Serum samples for serology will be collected at baseline and day 29. For pediatric subjects <10 kg, the serum sample for serology on the day 29 visit will not be collected due to restrictions in total blood volumes collection. For pediatric subjects <3 kg, the serum sample for serology on the baseline and day 29 visit will not be collected due to restrictions in total blood volumes collection.
9. The PK-ADA serum samples may be analyzed for ADA and NAb, if feasible.
10. Only for pediatric subjects who weigh ≥ 10 kg: The whole blood sample for RNA, should be collected on day 1/baseline (pre-dose). The whole blood for genomic DNA should be collected on day 1/baseline. If not collected at baseline, the sample for genomic DNA may be collected at any visit.

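### SAP 4.5.4 restricts the exploratory viral-load AUC in seropositive subjects to the seronegative mFAS, so its analysis set is empty; the seroconversion endpoint also needs its timing and denominator stated for cohort A1

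*SAP*

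**What the plan says.** **AUC.** The SAP 4.5.4 endpoint runs from the first positive NP swab "until the first confirmed negative test, in seropositive subjects (based on central lab test) that has an onset during the EAP". The note directly under it limits the analysis: "Only for RT-qPCR positive subjects during the EAP with confirmed negative tests in the seronegative mFAS". Protocol 4.1.4 gives the same population, "negative test, in seropositive subjects (based on central lab test) that has an onset during the EAP", and attaches no note. SAP 3.1 fixes serostatus as follows: "Seronegative is defined as all available test results are negative. Seropositive is defined as 1 or more available test results are positive". SAP 1.2.4 states that nothing differs from the statistical section of protocol amendment 6.

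**Seroconversion.** SAP 4.5.4 opens with "The following exploratory variables are for both Cohort A and Cohort A1". One entry is the proportion of baseline-seronegative subjects who become seropositive by Day 57. For children under 12, footnote 8 to the sampling schedule (SAP 10.2.4, repeated in Protocol 9.1.4) says "Serum samples for serology will be collected at baseline and day 29", then "For pediatric subjects <10 kg, the serum sample for serology on the day 29 visit will not be collected". Below 3 kg the baseline sample is omitted as well.

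**The concern.** An analysis rule that contradicts its own endpoint leaves the programmer to choose the population. Followed literally, this one returns an empty table. Otherwise someone decides, possibly after unblinding, whether to drop the note, keep part of it, or analyse the seronegative set instead. The SAP's stated purpose is to settle such choices before lock.

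The seroconversion entry raises a milder question. Cohorts A and A1 share one definition with a Day 57 horizon, but their blood-sampling schedules differ. The SAP does not say what the A1 figure represents or which children form its denominator.

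**Working it through.** No sample size, power or error rate is involved. The check is set logic and a reading of the schedules.

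**1. Can a subject be in both serostatus groups?** SAP 3.1 uses three assays, each of which can be negative, positive or unavailable.

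- Patterns with at least one available result: 3³ − 1 = 26.
- Seronegative (every available result negative): 2³ − 1 = 7.
- Seropositive (one or more positive): 26 − 7 = 19.
- Overlap: 0, since 7 + 19 = 26 uses every pattern once.

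Seropositive subjects within the seronegative mFAS therefore number 0.

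**2. The related viral-load entries side by side.**

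| Endpoint | Population | Note on analysis set | Consistent? |
|---|---|---|---|
| Secondary AUC, SAP 4.5.3 | Seronegative | Seronegative mFAS-A | Yes |
| Exploratory AUC, SAP 4.5.4 | Seropositive | Seronegative mFAS | No |
| Exploratory AUC, Protocol 4.1.4 | Seropositive | None | Yes |
| Two time-weighted averages, SAP 4.5.4 | Seropositive | None | Yes |

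The faulty note resembles the one in SAP 4.5.3, where it fits, so a carry-over is likely. That is an inference; the documents do not say so. The rest of the note adds little: the SAP 4.5.4 introduction already confines continuous variables to subjects with a positive central test in the EAP, and the endpoint itself ends at a confirmed negative.

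**3. Scheduled serology up to Day 57.**

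| Group | Baseline | Day 29 | Day 57 |
|---|---|---|---|
| Cohort A (Protocol Table 3) | Yes | Yes | Yes |
| A1, 10 kg or more | Yes | Yes | No |
| A1, 3 to under 10 kg | Yes | No | No |
| A1, under 3 kg | No | No | No |

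Paediatric Schedule D shows one further follow-up mark, at Day 113 in Protocol Table 6 and Day 85 in SAP Table 9 as extracted. That difference may be a table-reading artefact; either day is after Day 57 and does not alter the table above.

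In A1, children of 10 kg or more therefore supply a Day 29 result. Those from 3 to under 10 kg can be classed seronegative at baseline but have no scheduled later sample. Those under 3 kg have no scheduled baseline serology, so they would not normally meet the negative-antibody requirement of the mFAS-A1.

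**The case against.** The strongest reply is that this is one stray note in an exploratory list, and that its intent can be recovered from the protocol. That is fair as to consequence. It does not remove the contradiction, because the SAP is the document that will be programmed and it declares no departures from the protocol.

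Three stronger readings are tempting, and the documents do not support them.

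- *A reader might infer that viral burden in seropositive subjects yields no result at all.* It does: the two time-weighted averages in SAP 4.5.4 carry no such note and remain derivable.
- *A reader might infer that requiring a confirmed negative biases the comparison, because about 40% of placebo infections in the administrative assessment lasted 3 to 4 weeks and none on active drug lasted beyond 1 week (Protocol 3.2.6).* The protocol endpoint already ends at the first confirmed negative, so the requirement is not clearly new. Those durations come from seronegative subjects, 21 of them infected on placebo. A long infection is also not one without a confirmed negative: positive subjects are swabbed weekly beyond the EAP until two negatives or end of study (Protocol 9.1.1, footnotes 9 and 17). Neither document says how many in each arm would lack one.
- *A reader might infer that seroconversion cannot be derived, or that small children would count as non-converters.* The endpoint is cumulative. It is derivable in cohort A, and from Day 29 in A1 at 10 kg or more; SAP 10.2.6 also allows unscheduled serology in symptomatic subjects. No section classes a missing result as non-conversion.

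It is also true that the Protocol 4.1.4 lead-in names cohort A alone, under a heading naming both cohorts. That supports clarifying the A1 assignment.

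**Conclusion.** The AUC point holds: as written, 0 subjects qualify. This follows from the SAP's own definitions and needs no outside assumption.

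The A1 point holds as a clarification. The endpoint there is in effect a Day 29 measure at 10 kg or more. It has no scheduled follow-up sample from 3 to under 10 kg, and it is not like-for-like with cohort A. The documents do not give the number of children under 10 kg, so the extent cannot be stated.

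The importance is low. Both endpoints are exploratory, and SAP 5.7.4 plans no hypothesis tests in A1. No primary or key secondary result and no error rate is touched, and no size or direction of bias can be claimed.

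**What to change.** **AUC (SAP 4.5.4).** Replace the note with: *Only for baseline-seropositive, baseline RT-qPCR-negative subjects with at least one positive RT-qPCR during the EAP.* Report by arm the number without a confirmed negative test. AUC to the last available test may be added as a supportive summary, stating that it is truncated, and so understated, for subjects who had not cleared. The exclusion of administrative-assessment subjects from efficacy analyses still applies through SAP 7.

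**Seroconversion (SAP 4.5.4).** Keep the Day 57 horizon for cohort A. For A1, report a Day 29 result among baseline-seronegative children with a post-baseline serology result, give the number without one by weight group, and state that the figure is not to be compared directly with cohort A.

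**Cost.** Wording and table shells only, with no new data. The A1 definition, and the supportive AUC if added, go beyond the protocol text and should be recorded in SAP 1.2.4.
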